26. APR 2016

Date

Date

27 17 pr. 1 2016 Date

28 April 2016 Date

STUDY SYNOPSIS

Protocol 1VIT15042

Title: Randomized, placebo-controlled trial of ferric carboxymaltose in Restless Legs Syndrome patients with iron-deficiency anemia

Investigational Drug: Injectafer® (Ferric Carboxymaltose - FCM)

Treatment Phase I and II Primary Objective: To evaluate the efficacy and safety of FCM (750 mg dose x 2) for treatment of Restless Legs Syndrome (RLS) in patients with irondeficiency anemia (IDA).

Long-Term Extension Phase III Primary Objective: To evaluate the duration of effect of prior FCM treatment and to determine the effectiveness of further iron repletion with FCM when RLS symptoms worsen or reoccur.

Study Design: This will be a Phase II, randomized, placebo-controlled study. All subjects who meet the inclusion criteria, with no exclusion criteria, will qualify to enter the Screening Phase. The study will enroll 70 eligible subjects to receive blinded study drug in Treatment Phase I. All eligible subjects will be randomized in a 1:1 ratio to receive a blinded dose of either FCM 750 mg undiluted slow intravenous (IV) push at 100 mg/minute or a Placebo (15 ml of Normal Saline [NS]) IV push at 2 ml/minute on Day 0 and 7.

A subject will be defined at Day 42 as a **Responder** if the International Restless Legs Syndrome Severity Scale (IRLSS) score is ≤ 10 or if the IRLSS score is >10 with a Clinical Global Impression-Improvement (CGI-I) score of much or very much improvement and the subject does not request further treatment for RLS. A subject will be defined as a treatment **Non-Responder** if neither of these criteria are met.

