Primary efficacy endpoint in **Long-Term Extension Phase III** is to evaluate the duration of effect of FCM as defined as the number of weeks from the initial treatment without need for further treatment. Initial treatment is defined as Day 0 of Phase I for Responders in Phase I and Day 0 of Phase II for Responders in Phase II.

Secondary object is to determine the effectiveness (number of subjects who remain in the study) of additional FCM treatment, in the Long-Term Extension, in those who have worsening of RLS symptoms after the initial response.

Primary safety endpoint is to determine the safety of FCM in RLS patients with IDA

- Safety Evaluations will include:
 - Adverse events
 - Laboratory assessments, including hematology (Hgb, Hct, RBC, WBC, MCV, MCH, MCHC, RDW, platelets, differential count), iron indices (serum iron, serum ferritin, and total iron binding capacity (TIBC), percentage serum transferrin saturation (TSAT)), clinical chemistry (sodium, potassium, chloride, BUN, creatinine, albumin, alkaline phosphatase, total bilirubin, gamma-GGT, AST, ALT, LDH, calcium, phosphorus, glucose, bicarbonate)
 - Vital signs
 - Physical examinations.

Exploratory Aims:

- 1. Evaluate potential predictors of Day 42 (Treatment Phases I and II) treatment response using clinical, hematologic, and brain MRI data.
- 2. The change from baseline in MRI-determined iron concentration for other brain regions.
- 3. Correlation between changes in brain iron distribution and measures of peripheral iron status, RLS severity, and sleep quality.

- 4. Correlation between CBC, iron indices, and change from Baseline to Day 42 (Treatment Phases I and II) RLS severity, sleep, and PGI-I.
- 5. Correlation of baseline Vitamin D and post dose change in phosphate.
- 6. Vitamin D at each visit.

Inclusion Criteria:

- 1. Male or female subject ≥ 18 years of age who is able to give informed consent.
- 2. Confirmed diagnosis of RLS based on the Cambridge-Hopkins Diagnostic Questionnaire (CHDQ) and the Hopkins-Hening Telephone Diagnostic Interview (HDTI).
- 3. IRLSS score \geq 15 plus RLS symptoms for at least 3 months and currently occurring \geq 2 nights per week.
- 4. Iron-deficiency anemia defined as an Hgb <12 g/dl with a ferritin <20 ng/mL, or ferritin <100 when TSAT is <18%.
- 5. Subjects on sleep medication must be on a stable dose for at least 6 months prior screening.

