- 20. Any other pre-existing laboratory abnormality, medical condition, or disease that, in the opinion of Investigator, may cause the subject to be unsuitable for the study or place the subject at potential risk from being in the study, e.g. a malignancy, uncontrolled hypertension, unstable ischemic heart disease, or uncontrolled diabetes mellitus.
- 21. Subject is unwilling or has conditions that would prohibit them from complying with the study requirements.

RLS Therapy:

Subject should not be receiving treatment for RLS. All treatment for RLS should be discontinued at least 4 weeks prior to screening.

Study Duration – One year:

- Screening Phase: up to 14 days
- Treatment Phase I: 42 days
- Treatment Phase II: 42 days
- Long-term Extension Phase III: up to 46 weeks

Number of Subjects / Sample Size:

Enrollment is planned for completion (reaching Day 42 final assessment) of 70 randomized subjects (35 per treatment group). Based on Study 1VIT05009 in RLS subjects without IDA, approximately 50% of subjects in the FCM group and 15% of subjects in the placebo group are anticipated to have much or very much improvement on the CGI-I.³⁵ The proposed sample size provides >85% power to detect this difference with the chi-square test. The mean treatment difference and standard deviation of 5.0 (7.3) is estimated for change from Baseline to Day 42 for IRLSS score. The proposed sample size provides >80% power to detect this difference with the unpaired t-test.

Statistical Analyses:

The percentage responding to treatment will be evaluated for each drug condition in Treatment Phase I to determine the treatment difference at Day 42. This will be calculated from the IRLSS as change from Baseline and for the CGI-I with response determined as much or very much improved (scores of 1 or 2). All scores greater than 2 on the CGI-I are considered to indicate no significant response. For Phase II, the proportion of treatment non-responders in Phase I who respond to FCM in Phase II will be estimated and the IRLSS score, CGI-I, and PGI-I will be summarized at Day 42. The duration of treatment over the follow-up to end of study will be described as the percentage of responders and the IRLSS score change from Baseline at each time point. Time to first FCM dose after start of Phase III will be estimated with Kaplan-Meier methodology.

CONTACT PERSON FOR THE STUDY

For study related questions please contact:

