8.4 Endpoints and Definitions

8.4.1 Primary Endpoints

Treatment Phase I co-primary endpoints are:

- Change in IRLSS score from Baseline to Day 42 with comparison between FCM vs. Placebo, and
- Percentage of subjects who are much or very much improved at Day 42 as measured by the CGI-I.

Treatment Phase II primary efficacy endpoints are:

- IRLSS score change from Baseline (For Phase II the "baseline" is established on Day 42 of Phase I) compared to Day 42 in phase II.
- CGI-I at Day 42 in Treatment Phase II.

Long-Term Extension Phase III primary efficacy endpoints are:

• Estimate the time from first dose of FCM (Day 0 in either Phase I or Phase II) to time of FCM treatment intervention.

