8.5 Statistical Analyses of Efficacy

Categorical variables will be summarized with the number and percent of subjects in each treatment group with the characteristic. Quantitative variables will be summarized with the mean, median, standard deviation, minimum value, and maximum value. Baseline will be defined as the last value obtained before randomization.

Phase I

The treatment differences for the changing IRLSS score from Baseline to Day 42 will be assessed with the analysis of covariance with treatment as a fixed effect and baseline value as a covariate.

The treatment difference for the percentage of subjects who are much or very much improved at Day 42 as measured by the CGI-I will be assessed with the chi-square test.

Change from Baseline for IRLSS at Day 28, MOS at Day 42, and brain iron distribution at Day 42 will be assessed with the same method as IRLSS at Day 42. The percentage of subjects who are much or very much improved at Day 42 as measured by the PGI-I will be assessed with the chi-square test.

Phase II and III

All analyses will be descriptive.

For Phase II, the proportion of treatment **Non-Responders** in Phase I who respond to FCM in Phase II will be estimated and the IRLSS, CGI-I, PGI-I and brain iron distribution will be summarized at Day 42.

The Kaplan-Meier method will be used to estimate time from first dose of FCM to treatment intervention. Subjects in Phase III who discontinue the study before requiring treatment intervention will be censored on the day of the last contact with the Investigator.

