6.1.3 Phase III: Time from initial FCM treatment to further FCM treatment

Time (weeks) from the initial FCM treatment to further FCM treatment received in Phase III will be calculated as the integer of $(\text{date of the further FCM treatment in Phase III} - \text{date of the initial FCM treatment}) / 7 + 1$. The time duration will be summarized via descriptive statistics including number of subjects, median, minimum (min) and maximum (max). Initial treatment is defined as Day 0 of Phase I for responders in Phase I and Day 0 of Phase II for responders in Phase II. At any time before week 46 subject could receive a single dose of unblinded FCM treatment (i.e. the further FCM treatment) if RLS symptom is worsened.

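### The Phase III duration summary pools subjects with no FCM, one FCM course and two FCM courses before entry, so it is not the duration of effect of any one exposure

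*Protocol*

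**What the plan says.** The Phase III objective in the Protocol synopsis begins "To evaluate the duration of effect of prior FCM treatment". The primary endpoint is duration of effect, "defined as the number of weeks from the initial treatment without need for further treatment". The synopsis then fixes the start of the clock: "Initial treatment is defined as Day 0 of Phase I for Responders in Phase I and Day 0 of Phase II for Responders" of that second phase. SAP 1.2.1 and 6.1.3 repeat this ("Initial treatment is defined as Day 0 of Phase I for responders in Phase I and Day 0 of Phase II for responders" of that second phase), and SAP 2.1 sets the Phase III baseline the same way.

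SAP 6.1.3 calculates "Time (weeks) from the initial FCM treatment to further FCM treatment received in Phase III" and summarises it once, by n, median, minimum and maximum. It names no split by Phase I arm or by amount of FCM received. SAP 2.1 shows treatment group for Phase I only.

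Elsewhere the Protocol words the starting point differently:

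- Synopsis, Statistical Analyses: "Time to first FCM dose after start of Phase III will be estimated with Kaplan-Meier methodology".
- Section 8.4.1: "Estimate the time from first dose of FCM (Day 0 in either Phase I or Phase II) to time of FCM treatment intervention".
- Section 8.5: "The Kaplan-Meier method will be used to estimate time from first dose of FCM to treatment intervention".

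Phase II admits Phase I Non-Responders from both arms if they meet the laboratory criteria, and gives each a further 750 mg on Day 0 and Day 7. Responders from Phase I (either arm) and from Phase II continue into Phase III.

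**The concern.** A subject randomised to FCM who is a Non-Responder at Day 42 can be given a second FCM course and, if then a Responder, enters Phase III. The clock starts at Phase II Day 0, so the reported time describes what followed two courses. The need for further FCM after the first course is not counted in this endpoint.

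A Phase I placebo Responder enters the same summary with Phase I Day 0 as the initial FCM treatment date, although that dose was saline. Any FCM this subject receives in Phase III is a first exposure, not a repeat.

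A single median over these groups and the one-course Responders cannot be read as the duration of effect of a defined FCM exposure. Because SAP section 6 makes every phase descriptive, that summary is the whole Phase III primary result.

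**Working it through.** **Dose per route.** Protocol 3.2 gives 1,500 mg as the total for one course, which reproduces: 2 x 750 = 1,500 mg. Two courses: 4 x 750 = 3,000 mg.

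**Clock shift.** Phase II Day 0 falls within 7 days of the Day 42 visit, so 42 + 0 to 42 + 7 = 42 to 49 days (6 to 7 weeks) after Phase I Day 0. If the 3-day window for Day 42 in SAP Table 1.1 is used in full, the upper end is 45 + 7 = 52 days.

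**Expected numbers.** From Protocol 8.1: 35 per arm, with 50% (FCM) and 15% (placebo) much or very much improved on the CGI-I. Assumptions that the documents do not supply:

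- the CGI-I rates stand in for Responder status;
- 30% to 100% of FCM-arm Non-Responders meet the laboratory criteria, and 20% to 50% of those respond to the second course;
- all placebo Non-Responders are eligible and 50% respond.

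Phase I Non-Responders: FCM 35 - 17.5 = 17.5; placebo 35 - 5.25 = 29.75.

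| Route into Phase III | FCM before Phase III | Clock starts at | Expected n |
|---|---|---|---|
| Phase I Responder, FCM | one course, 1,500 mg | Phase I Day 0, first FCM dose | 35 x 0.50 = 17.5 |
| Phase II Responder, ex-placebo | one course, 1,500 mg | Phase II Day 0, first FCM dose | 29.75 x 1.0 x 0.5 = 14.9 |
| Phase II Responder, ex-FCM | two courses, 3,000 mg | Phase II Day 0, start of second course | 17.5 x 0.3 x 0.2 = 1.05 to 17.5 x 1.0 x 0.5 = 8.75 |
| Phase I Responder, placebo | none | Phase I Day 0, saline | 35 x 0.15 = 5.25 |

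One-course total: 17.5 + 14.9 = 32.4.

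Two-course share of all entrants:

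- low: 1.05 / (32.4 + 5.25 + 1.05) = 1.05 / 38.7 = 2.7%
- high: 8.75 / (32.4 + 5.25 + 8.75) = 8.75 / 46.4 = 18.9%

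Two-course share of entrants given FCM before Phase III: 1.05 / 33.4 = 3.1% to 8.75 / 41.1 = 21.3%.

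Placebo Responders as a share of all entrants: 5.25 / 46.4 = 11.3% to 5.25 / 38.7 = 13.6%.

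**Protocol wordings side by side.** Take a two-course subject re-dosed T weeks after Phase II Day 0. Day 0 of the responding phase gives T. First dose of FCM (8.5, read literally) gives T + 6 to T + 7. Start of Phase III, taken as Phase II Day 42, gives T - 6. The parenthesis in 8.4.1 allows either of the first two. Read literally, the wordings are 12 to 13 weeks apart for this subject.

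**The case against.** The strongest reply is that restarting the clock is reasonable. The endpoint is conditional on response, and Day 0 of the phase in which the subject responded gives the duration after the course that worked. This stands. A reader might infer that the starting point itself is wrong; the documents do not support that, and the fix keeps it.

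A reader might also infer that first-course failures vanish from the report. They do not. Protocol 8.4.2 estimates Phase II response among Phase I Non-Responders by randomised group. SAP 6.2.2 has a dedicated IRLSS summary for FCM-arm Non-Responders, and SAP 6.2.6 and 6.2.7 report response by Phase I group. The failure is missing only from the duration endpoint.

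Nor do the documents promise a duration specific to 750 mg x 2. That regimen is named in the Phase I and II objective, while the Phase III objective names no dose. Protocol 3.1 does put the 750 mg x 2 dose and the long-term need for further dosing in one sentence, so a reader may well attach the figure to that regimen. Even without that label, the mixture remains.

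The 12-to-13-week spread is a difference in Protocol wording, not an ambiguity in the planned analysis, because the SAP uses one starting point throughout. The Protocol reviewed here dates from April 2016 and the SAP cites one of 4 September 2019, so later text may already be aligned.

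Finally, the shares above are of Phase III entrants. SAP 6.1.3 summarises a time to further FCM received, and a subject never re-dosed has no such time. The shares among those summarised may differ.

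**Conclusion.** The point holds as one of interpretation. The planned duration summary pools zero, one and two FCM courses before Phase III and is not the duration of effect of any one of them.

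At planned enrolment and under the assumptions shown, the pool holds about 1 to 9 two-course subjects (3% to 19% of all entrants, or 3% to 21% of those given FCM before Phase III) and about 5 placebo Responders, beside about 32 one-course subjects. The laboratory-eligibility and Phase II response rates are assumed. SAP section 9 reports early termination, and enrolment short of plan would lower the counts. Neither the size nor the direction of any effect on the median can be derived from the documents.

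No error rate, power figure or Phase I comparison is touched: Phase III was descriptive in Protocol 8.5, and SAP sections 6 and 9 drop formal testing of the primary endpoints in all phases.

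**What to change.** 1. Keep the SAP starting point: Day 0 of the phase in which the subject was classed as Responder. Align the synopsis (Statistical Analyses) and Protocol 8.4.1 and 8.5 with it, or confirm that the 2019 protocol already does so.
2. In SAP 6.1.3, report duration in separate rows by number of FCM courses received before Phase III:
   - zero: Phase I placebo Responders, labelled as time from saline to first FCM;
   - one: Phase I FCM Responders and ex-placebo Phase II Responders;
   - two: ex-FCM Phase II Responders.
3. Interpret only the one-course row as the duration after FCM 750 mg x 2.
4. Print beside it the n (%) of Phase I FCM subjects who were given a second course in Phase II.

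The cost is a few lines of wording and extra rows in one table, from data already collected. No treatment rule changes. The drawback is that the zero- and two-course rows will be small and can only be described.

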4.5 Endpoints in participation / Early termination endpoints

Termination in participation is defined as:

- 1. The subject is considered a treatment Non-Responder (see definition of non-responder below) as assessed at Day 42 of Treatment Phase I and is not eligible for Treatment Phase II.
- 2. The subject is considered a treatment Non-Responder (see definition of non-responder below) as assessed at Day 42 of Treatment Phase II.
- 3. The subject in Long-Term Extension Phase III who has "worsening of RLS" by definition but cannot receive further iron treatment because laboratory criteria are not met and wishes to have alternative treatment for RLS.
- 4. The subject in Long-Term Extension Phase III who wishes to have alternative treatment for RLS other than FCM.
- 5. Completes Long-Term Extension Phase III.

Endpoints for early termination is defined as:

- 1. Significant adverse effect during the treatment period.
- 2. Significant adverse event or health issues after starting the iron treatment, and before the final evaluation that was judged to require ending the study.
- 3. Subject decision not to continue in the study after the treatment and before the final evaluation.
- 4. The Principal Investigator has determined it would be harmful to the subject to continue in the study.
- 5. Subject is non-compliant with study requirements.
- 6. Use of other medications to treat RLS, other than study medication.

4.6 Treatment Responder and Non-Responder:

Subject will have been determined to have met the definition of Responder when the IRLSS score is ≤ 10 or a >10 with a CGI-I score of much or very much improvement and the subject does not request further treatment for RLS. Subjects who do not meet the primary endpoint will be deemed treatment Non-Responders.

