8.4.2 Secondary Endpoints

Phase I and Phase II:

- Change in IRLSS score from Baseline to Day 42. (Treatment Phase I and II)
- IRLSS score change from Baseline (For Phase II the "Baseline" is established on Day 42 of Phase I) compared to Day 42 of Treatment Phase II.
- CGI-I and PGI-I at each visit and percentage of subjects who are much or very much improved at Day 42. (Treatment Phase I and II)
- Change in sleep quality (MOS Sleep) from Baseline to Day 42. (Treatment Phase I and II)
- Estimate the proportion of treatment non-responders in Phase I who respond to FCM in Phase II for each randomized treatment group. (Phase II only)
- Change in substantia nigra iron index from Baseline to Day 42. The index will be determined using measures of MRI relaxation rate (R2*) or Quantitative Susceptibility Mapping (QSM). (Treatment Phase I and II)
- Change in iron index (R2* or QSM) for thalamus and motor cortex from Baseline to Day 42. (Treatment Phase I and II).

Phase III:

- Change in IRLSS from Baseline to each scheduled assessment.
- Number of subjects who remained in the study to Week 52.

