2.4 HANDLING OF MISSING DATA

Missing data will not be imputed for descriptive statistical summaries in safety or efficacy analyses.

For the PGI-I score, missing data at Day 42 will be considered as failure in analysis.

Dates missing the day or both day and month of the year will adhere to the following conventions to classify TEAE and to classify prior/concomitant medications.

- A medication with a completely missing start date will be considered a prior medication. A medication with a completely missing stop date will be considered a concomitant medication.
- If complete AE onset date is missing and AE end date is on or after the first dose date then it will be counted as a treatment emergent AE (TEAE) for the study. If complete AE onset date is missing and AE end date is before the first dose date then it will be counted as a not treatment emergent AE (TEAE) for the study.
- If an AE or a medication has a partial missing start or stop date, the following rules will be used for imputation:
 - If year is present but month and day are missing, impute start date as January 1 of that year or first dose date if the year is the same as the year of first dose date and impute stop date as December 31 of that year.
 - If year and day are present but month is missing, impute start month as January or the month of the first dose date if the year and day is the same as the year and day of first dose date and impute stop month as December.
 - If year and month are present but day is missing, impute start date as first day of that month or first dose date if the year and month are the same as the year and month of first dose date and impute stop date as last day of that month.

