The number (percentage) of treatment responders at Day 42 of Phase I and Phase II will be summarized by treatment group in Phase I, separately. The subjects who missing responder/non-responder classification will be considered as non-responder.

6.2.8 Phase I and Phase II: Change in substantia nigra iron index from baseline to Day 42

The actual value of substantia nigra iron index on baseline and Day 42, and change from baseline to Day 42 will be summarized via descriptive statistics by treatment group (for Phase I only) for each treatment phase.

Substantia nigra iron index will be measured using MRI relaxation rate (R2*) or QSM.

6.2.9 Phase I and Phase II: Change in thalamus and motor cortex iron index from baseline to Day 42

The actual value of thalamus and motor cortex iron index on baseline and Day 42, and change from baseline to Day 42 will be summarized via descriptive statistics by treatment group (for Phase I only) for each treatment phase, separately.

Iron index will be measured using MRI relaxation rate (R2*) or QSM.

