6.2.10 Phase III: Change in IRLSS total score from baseline to each visit

The actual value of IRLSS total score on baseline and each scheduled visit (i.e. Weeks 15, 25, 34, 43 and 52 via phone contact), and change from baseline to each scheduled visit will be summarized via descriptive statistics.

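### Phase III durability is shown by week only as observed-case IRLSS change, so loss of response in subjects who leave for other RLS treatment appears in no weekly efficacy summary

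*Protocol*

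**What the plan says.** - **Protocol synopsis, Statistical Analyses.** Follow-up to the end of study is to be "described as the percentage of responders and the IRLSS score change from Baseline at each time point". No denominator is given, and no rule for subjects who have left.
- **Protocol 8.4.2.** The by-visit Phase III endpoint is "Change in IRLSS from Baseline to each scheduled assessment". The only other Phase III secondary endpoint is the number remaining to Week 52. Section 8.5 adds no Phase III responder percentage.
- **SAP 6.2.10.** IRLSS at Weeks 15, 25, 34, 43 and 52, and the "change from baseline to each scheduled visit will be summarized via descriptive statistics".
- **SAP 6.2.7.** "The number (percentage) of treatment responders at Day 42 of Phase I and Phase II will be summarized by treatment group in Phase I". Neither this section nor 6.2.6 extends responder status into Phase III.
- **SAP 2.4.** "Missing data will not be imputed for descriptive statistical summaries in safety or efficacy analyses".
- **Protocol 4.5.** Participation ends for a Phase III subject with worsening who "cannot receive further iron treatment because laboratory criteria are not met and wishes to have alternative treatment for RLS", and for any Phase III subject "who wishes to have alternative treatment for RLS other than FCM". Use of other RLS medication is also an early-termination endpoint.

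**The concern.** Duration of effect is the Phase III primary objective. The exit rules tie leaving to poor RLS control, and the by-visit mean is taken over whoever is still being assessed. Such a mean can hold steady, or even improve, while subjects lose response and leave. A reader would see a flat IRLSS curve and take it as durable benefit. This arises even if nobody receives further FCM, so it is separate from the mixing of scores taken before and after re-dosing.

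**Working it through.** The documents give no Phase III relapse rate, dropout rate or expected mean, so there is no planned figure to reproduce. The check has two parts: where a leaver appears in the planned output, and the direction of the effect.

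**Where a subject who worsens and leaves without further FCM appears**

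| Planned output | What it shows for this subject |
|---|---|
| By-visit IRLSS (SAP 6.2.10) | Contributes until exit, then absent |
| Time to further FCM (SAP 6.1.3) | No value: the time is calculated from the date of further FCM, and no censoring is stated |
| Kaplan-Meier estimate (Protocol 8.5) | Censored at last contact, not counted as loss of response |
| Responder tables (SAP 6.2.6, 6.2.7) | Day 42 of Phases I and II only |
| Disposition (SAP 3.1, SAP 9 item 3) | Counted as a discontinuation, with reason; not linked to response by week |
| Further FCM (SAP 5.1) | Counted as not re-dosed |

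Protocol 4.4 asks for final procedures at withdrawal, so an exit score may exist. SAP 2.3 tabulates scheduled visits only, so a score from an unscheduled exit visit would not reach the table.

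**Direction and form of the bias**

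Let s be the share of entrants who have left, and g the amount by which stayers' mean improvement exceeds the improvement leavers would have shown. The all-entrant mean is (1 - s) x stayer mean + s x leaver mean. The observed-case mean therefore overstates improvement by s x g.

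With assumed ranges s = 0.10 to 0.30 and g = 5 to 12 points:
- lowest: 0.10 x 5 = 0.5 points
- highest: 0.30 x 12 = 3.6 points

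A worked case, with all inputs assumed: 30 entrants, mean change -15 if response is held and -5 if lost, no re-dosing.

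| Lost response | All-entrant mean | Observed mean, half of these leave | Observed mean, all of these leave |
|---|---|---|---|
| 20% | -13.0 | -13.9 | -15.0 |
| 40% | -11.0 | -12.5 | -15.0 |
| 60% | -9.0 | -10.7 | -15.0 |

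For the 40% row with half leaving, 18 hold, 6 lose response but stay, and 6 leave. The observed mean is (18 x -15 + 6 x -5) / 24 = -12.5. The all-entrant mean is (18 x -15 + 12 x -5) / 30 = -11.0. The difference is 1.5, which equals s x g = 0.20 x 7.5. If all who lose response leave, the observed mean stays at -15.0 whatever the relapse rate, and the overstatement is 2.0, 4.0 or 6.0 points.

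**Would the responder percentage alone cure this?** Only with the right denominator. In the same case, the percentage over all entrants is 80%, 60% and 40%. Over those still observed it is 89%, 75% and 57% if half leave, and 100% throughout if all leave.

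**Can the Day 42 responder definition be reused?** No. It needs CGI-I when IRLSS is above 10, and Protocol Table 3.2.2 schedules no CGI-I in Phase III.

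**The case against.** The strongest reply is that this is a mismatch between the synopsis and the body of the protocol: SAP 6.2.10 matches Protocol 8.4.2, and the synopsis sentence never specified an all-entrant percentage. That stands. Several stronger readings that a reader might infer are not supported:

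- **That a planned all-entrant analysis was dropped.** The synopsis gives no denominator. Read as observed-case, the promised percentage would carry the same selection.
- **That SAP 9 conceals the change.** SAP 9 compares with a protocol dated 4 September 2019. The protocol available here carries April 2016 dates, so whether the sentence survived cannot be checked.
- **That leavers disappear from the report.** Completers, reasons for discontinuation and re-dosing are all counted. SAP 2.1 already prints the number of subjects with each mean.
- **That every subject who worsens leaves.** Failing the laboratory criteria ends participation only if the subject also wants other treatment. Those who want nothing else stay and contribute their scores. Those who qualify may be re-dosed and stay.
- **That the bias can be set against the planned difference of 5.0 points.** That figure is the Phase I FCM-placebo difference at Day 42. Phase III has no concurrent control.

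It is also fair that by-visit IRLSS is secondary, that all Phase III analyses are descriptive, and that the study ended early. No type I error or power is affected. What remains is that disposition counts do not tell a reader, week by week, how many entrants still have their response.

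**Conclusion.** The point holds as a moderate one about interpreting durability. The synopsis names two by-visit measures; Protocol 8.4.2 and the SAP carry one, without imputation, under exit rules linked to outcome. Later means are selected toward subjects still doing well, provided that those who leave for other RLS treatment have worse IRLSS than those who stay. The exit rules make that likely but do not guarantee it.

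The size is unknown. The 0.5 to 3.6 points and the worked case show direction and form only; every input is assumed.

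**What to change.** 1. Reconcile the synopsis sentence with Protocol 8.4.2 and SAP 6.2.10.
2. In SAP 6.2.10, beside the observed-case mean, add the number and percentage of Phase III entrants with **response maintained** at each scheduled week. For this analysis that means: no worsening so far by the plan's own criterion (an IRLSS rise of more than 4 points from the last evaluation captured), no further FCM, and no exit for worsening or for other RLS therapy. Derive status from every evaluation captured up to that week, including unscheduled and exit scores, as a stated exception to SAP 2.3.
3. Add a second row for IRLSS of 10 or less, counting those who left for these reasons as not in response. It is needed because the criterion looks back only one evaluation: rises of 4 points at each of five contacts would add 5 x 4 = 20 points without meeting it. Label this row as including any effect of re-dosing, and print its Day 42 value, since some responders enter above 10.
4. Use as denominator all entrants due to reach that week before study termination. Show subjects missing for unrelated reasons on their own line.
5. Record the addition in SAP 9.

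These are reporting definitions and change nothing about who is treated. Counting leavers as not in response follows SAP 6.2.6 and 6.2.7, which already treat a missing classification as non-response.

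The cost is one or two descriptive rows, with no new data collection provided the recorded exit reasons separate these cases. The count is conservative, so it should be read together with the observed-case mean.
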